To calculate the power for the acute effects of the study three analyses are considered using the paired differences of subjects at baseline and acute time points. A two-sample test on the means is performed using: Wilcoxon test (non-parametric), T-test (parametric) and a Bayesian (parametric) approach. While from a Bayesian paradigm the notion of power does not exist in the traditional sense, one can create a decision rule and loss function in such a way that the associated risk is analogous to the notion of power. To understand the power of each of the methods a Monte Carlo study was performed

n1	Test	Percent Change			
		Low (10%)	Medium (25%)	High (50%)	75%
4	T-test	0.116	0.448	0.955	0.998
	Wilcoxon	0.044	0.242	0.855	0.992
	Bayesian	0.249	0.689	0.992	1
6	T-test	0.138	0.528	0.981	0.999
	Wilcoxon	0.079	0.357	0.941	0.997
	Bayesian	0.308	0.782	0.994	1
8	T-test	0.116	0.588	0.986	1
	Wilcoxon	0.096	0.495	0.956	1
	Bayesian	0.309	0.803	0.999	1

Wilcoxon and Bayesian Power are based off of 1,000 Monte Carlo simulations.

utilizing 1,000 separate datasets for likely effect sizes and sample sizes. The power was calculated as the proportion of datasets in which the test “rejected” the null hypothesis. The table below gives the power for each test across percent change in effect size and control group sample sizes, here the treatment group sample size was $n_2 = 12$. Based on the table at left, an n of 6 was chosen as the sample size for the placebo group.

BACKGROUND

Lorcaserin is a 5-HT_{2C}R agonist (Trade Name Belviq) approved for treatment of obesity.

Overview of Non-Clinical Studies

Lorcaserin and other 5-HT_{2C}R agonists have been shown to reduce cocaine self-administration and cue reactivity in rodents (Cunningham et al., 2011; Manvich et al., 2012). We have collected preliminary data to

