Up to 18 eligible patients will be randomly assigned to lorcaserin or placebo treatment groups in a 1:2 ratio using a SAS-based computer-generated randomization scheme developed by the study data management provider.

Blinding

Due to the objectives of the study, the identity of test and control treatments will not be known to investigators, research staff, or patients. The following study procedures will be in place to ensure double-blind administration of study treatments.

Access to the randomization code will be strictly controlled.

Packaging and labeling of lorcaserin and placebo will be identical to maintain the blind.

Lorcaserin concentrations will not be analyzed till the end of the study.

The study blind will be broken on completion of the clinical study and after the study database has been locked.

During the study, the blind may be broken only in emergencies when knowledge of the patient's treatment group is necessary for further patient management. Unblinding will occur by the PI contacting the research pharmacy to break the blind in case of emergency.

Formulation of Test Product

Lorcaserin HCL 10mg tablets (Belviq, Arena Pharmaceuticals) will be used for this study. To ensure blinding, tablets will be placed in gelatin capsules by the research pharmacist prior to administration.

Commercially available sterile normal saline for human use will be used as a matched placebo for cocaine. Cocaine is packaged in 2 mL vials containing 20 mg per mL.

Cocaine for IV human use will be obtained from a NIDA contractor under a letter of authorization to allow cross reference to NIDA's DMF for cocaine obtained and submitted to the IND.

The pharmacist will prepare the cocaine according to instructions supplied by the NIDA contractor and dispense according to the randomization. The labels on the cassettes of cocaine and matching placebo will conform to internal Pharmacy and CRSU SOPs and instructions.

The doses of cocaine will be prepared by diluting cocaine with 20 mL normal saline.

Cocaine administration: Cocaine will be administered by a study nurse under the direct supervision of a physician. The drug is given intravenously (IV) over a 2 minute period in a cassette via a pump delivery system.

Formulation of Control Product

Gelatin placebo capsules identical to capsules that enclose the study drug will be used for placebo. Dextrose powder will be used as a filling in the capsules.

Packaging and Labeling

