Each pill bottle of study drug will be labeled with the required FDA warning statement, the protocol number, a treatment number, the name of the study physician, and directions for patient use and storage.

Administration of Study Drug

Dosage/Dosage Regimen

If subjects meet inclusion criteria, they will be seen both in the hospital and at IDAS clinic for a total of 12 active study days and monitoring procedures will be in place to detect drug and alcohol use and assess for adverse events at each visit. In addition, the hospital cocaine administration procedures will reduce the likelihood of increased cocaine craving after cocaine administration. Subjects will undergo procedures as described below. Subjects will not be allowed to smoke cigarettes, as smoking is not allowed in the hospital or anywhere on the VCU campus. Subjects will have the option to use a nicotine patch dosed based on the amount of daily cigarettes smoked. Subjects will not be allowed to leave the CRS Unit nor receive visitors during their study visits. Subjects who are unable to comply with these restrictions will be dropped from the study. After a screening cocaine infusion to determine safety, eligible subjects will be randomized to Group A –placebo only or Group B –placebo followed by an ascending dose of lorcaserin. Six subjects will be assigned to Group A (placebo) and 12 subjects will be assigned to Group B (active lorcaserin).

Study Drug Dosage: Lorcaserin will be 10mg once daily increasing to 10mg twice daily.

Outcome Measures: The primary outcome measures are adverse events, cardiovascular responses (Heart rate (HR), blood pressure (BP), ECG measurements, subjective response to cocaine, cocaine self-administration, and cocaine blood PK. Secondary outcome measures will be impulsivity as measured by the immediate memory task (IMT).

- 1) Days 1-2: All subjects will be seen on the CRSU. All subjects will receive placebo on days 1-2 in a single blind fashion. Vital signs including heart rate, blood pressure and respiration rate will be obtained after placebo administration. Days 1-2 will be single-blind placebo, whereas all remaining study days will be double-blind. All subjects will leave the CRSU at the end of each study day.

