Adverse event rates will be coded by body system and MedDra classification term. Adverse events will be tabulated by treatment group and will include the number of patients for whom the event occurred, the rate of occurrence, and the severity and relationship to study drug.

Interim Analysis

When approximately 50% of patients have completed the study, an interim analysis for safety will be conducted by the DSMB. Serious adverse events will be monitored by the committee on an ongoing basis throughout the study.

Sample Size and Randomization

This project requires a final sample size of 18 subjects (Six subjects assigned to Group A (placebo) and 12 subjects assigned to Group B (active lorcaserin)). This sample size for effect of lorcaserin on cocaine self-administration was based on previous research showing effects of medication on human cocaine self-administration (Hart et al, 2008). In an effort to increase the power of the study, a Bayesian approach will also be utilized that incorporates information from previous studies. This approach will use a Bayesian hierarchical model with subject at the lowest level of the hierarchy and treatment group at the second level. This model is analogous to the repeated measures ANOVA except that prior information will be introduced. Since many similar studies have been conducted with cocaine users and the same outcome measures we will assign an

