informative prior distribution on the control group where the mean and standard deviation are educated guesses from the information provided in previous study of Hart et al. (2008). For the treatment group we will assume a priori no change in the mean from the control group and the standard deviation are similar to those as the experimental group of the study by Hart et al. (Hart et al, 2008). The model will be calculated using standard Markov Chain Monte Carlo (MCMC) packages such as WinBUGS, OpenBUGS, JAGS or MCMCpack in R. Because MCMC sampling techniques are being employed the quality of the samples from the posterior distribution will be checked using trace plots, effective sample size, potential scale reduction factor and Hellinger distances (for more on Bayesian analyses and MCMC sampling see (Gelman et al, 2013). As necessary techniques such as discarding burn-in samples, thinning and over-disperse starting points will be employed in order to obtain a set of samples from the posterior distribution that have an effective sample size of 10,000 on all parameters. All inferences will be made from this set of samples from the posterior distribution.

To calculate the power for the acute effects of the study three analyses are considered using the paired differences of subjects at baseline and acute time points. A two-sample test on the means is performed using: Wilcoxon test (non-parametric), T-test (parametric) and a Bayesian (parametric) approach. While from a

n1	Test	Percent Change				
		Low (10%)	Medium (25%)	High (50%)	75%	100%
4	T-test	0.116	0.448	0.955	0.998	1
	Wilcoxon	0.044	0.242	0.855	0.992	1
	Bayesian	0.249	0.689	0.992	1	1
6	T-test	0.138	0.528	0.981	0.999	1
	Wilcoxon	0.079	0.357	0.941	0.997	1
	Bayesian	0.308	0.782	0.994	1	1
8	T-test	0.116	0.588	0.986	1	1
	Wilcoxon	0.096	0.495	0.956	1	1
	Bayesian	0.309	0.803	0.999	1	1
Wilcoxon and Bayesian Power are based off of 1,000 Monte Carlo simulations.						

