Bayesian paradigm the notion of power does not exist in the traditional sense, one can create a decision rule and loss function in such a way that the associated risk is analogous to the notion of power. To understand the power of each of the methods a Monte Carlo study was performed utilizing 1,000 separate datasets for likely effect sizes and sample sizes. The power was calculated as the proportion of datasets in which the test “rejected” the null hypothesis. The table below gives the power for each test across percent change in effect size and control group sample sizes, here the treatment group sample size was $n_2 = 12$. Based on the table at left, an n of 6 was chosen as the sample size for the placebo group.

DATA COLLECTION, RETENTION AND MONITORING

Data Collection Instruments

The Investigator will prepare and maintain adequate and accurate source documents designed to record all observations and other pertinent data for each subject treated with the study drug.

Study personnel at each site will enter data from source documents corresponding to a subject’s visit into the protocol-specific paper CRF when the information corresponding to that visit is available. Subjects will not be identified by name in the study database or on any study documents to be collected by the Sponsor (or designee), but will be identified by a subject number.

The Investigator is responsible for all information collected on subjects enrolled in this study. All data collected during the course of this study must be reviewed and verified for completeness and accuracy by the Investigator.

Data Management Procedures

The data will be entered into a REDCap database. The Data Management group will be responsible for data processing, in accordance with procedural documentation. Database lock will occur once quality assurance procedures have been completed.

All procedures for the handling and analysis of data will be conducted using good computing practices meeting FDA guidelines for the handling and analysis of data for clinical trials.

Data Quality Control and Reporting

After data have been entered into the study database, a system of computerized data validation checks will be implemented and applied to the database on a regular basis. The study database will be updated in accordance with the resolved queries. All changes to the study database will be documented.

Archival of Data

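### The randomisation sentence allocates lorcaserin or placebo 1:2, but every arm size in the plan is 12 lorcaserin and 6 placebo, which is 2:1

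*Combined protocol and SAP*

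**What the plan says.** Study Treatments, Method of Assigning Subjects to Treatment Groups, specifies a SAS-based computer-generated scheme and gives its ratio: "Up to 18 eligible patients will be randomly assigned to lorcaserin or placebo treatment groups in a 1:2 ratio". No counts are attached, and the two parts of the ratio are not labelled.

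The other statements of arm size are:

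- Dosage/Dosage Regimen, under the same Study Treatments heading: "eligible subjects will be randomized to Group A –placebo only or Group B –placebo followed by an ascending dose of lorcaserin", and then "Six subjects will be assigned to Group A (placebo) and 12 subjects will be assigned to Group B (active lorcaserin").
- Sample Size and Randomization, as the breakdown of the final 18: "Six subjects assigned to Group A (placebo) and 12 subjects assigned to Group B (active lorcaserin").
- The power text, in the synopsis (Rationale for Number of Subjects) and again in Sample Size and Randomization: the simulation fixes the treatment group at 12, and "an n of 6 was chosen as the sample size for the placebo group".

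**The concern.** A ratio that follows two named arms is normally read in the order of the names. Read that way, the sentence defining the randomisation reverses the design that the rest of the plan describes and powers. A programmer at the data management provider could reasonably work from this sentence alone. Blinded site staff would have little chance of noticing a reversed list: under Blinding, access to the code is strictly controlled and, emergencies aside, the blind is broken only after database lock.

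A reversal would mainly affect the outcomes that depend on the number given lorcaserin:

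- Interaction safety is a primary objective, and Risks of Lorcaserin Combined with Cocaine says the combination has not been studied in humans.
- Cocaine PK (Primary Efficacy Endpoint, item 4) is compared within subjects between Day 2 on placebo and Days 6 and 10 on lorcaserin. Only lorcaserin-group subjects contribute to that contrast.

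Detection of serious events does not hang on the 50% safety look alone: "Serious adverse events will be monitored by the committee on an ongoing basis throughout the study". What would be lost is exposure and precision.

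**Working it through.** **Inputs.** N = 18 (Study Overview; Sample Size and Randomization). Ratio 1:2 for lorcaserin or placebo (Method of Assigning Subjects). Arms 12 lorcaserin and 6 placebo (Dosage/Dosage Regimen; Sample Size and Randomization). Stated t-test power with 6 placebo and 12 treated: 0.138, 0.528, 0.981 and 0.999 at 10%, 25%, 50% and 75% change (power table). The documents give no alpha, SD or absolute effect for that table.

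**1. Arm sizes.**

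- Ratio as written, in the order named: 18 × 1/3 = 6 lorcaserin; 18 × 2/3 = 12 placebo.
- Counts stated elsewhere: 12 lorcaserin + 6 placebo = 18, so lorcaserin:placebo = 2:1.
- Group A:Group B = 6:12 = 1:2. The written ratio is therefore correct for placebo:lorcaserin, which points to transposed labels.

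Two other sets of numbers are not competing arm sizes. The 8 and 8 patients in Table 3 are session-order columns. The values 4, 6 and 8 in the power table are candidate placebo sizes, from which 6 was chosen.

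**2. The plan's power figure.** For a pooled two-sample t-test at two-sided alpha 0.05 (assumed), the effect that reproduces 0.528 with 6 and 12 is 1.08 SD. Scaling it to the other changes gives:

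| Change | Stated | Recomputed |
|---|---|---|
| 10% | 0.138 | 0.129 |
| 25% | 0.528 | 0.528 (calibrated) |
| 50% | 0.981 | 0.982 |
| 75% | 0.999 | 1.000 |

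This row of the table is consistent with such a test. It is a consistency check, because the effect was back-solved from one entry.

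**3. Power if the arms are reversed.** The standard-error factor is √(1/6 + 1/12) = √(1/12 + 1/6) = 0.500, and df = 6 + 12 − 2 = 16, either way. Power at the 25% change is 0.528 for both splits. With equal variances this holds at any alpha. It fails if the arm SDs differ. In simulation with the lorcaserin SD twice the placebo SD and an effect of 1.08 placebo SDs, Welch t-test power was 0.296 with 12 on lorcaserin and 0.191 with 6. With half the placebo SD it was 0.565 and 0.812, so the direction depends on SDs that are not given.

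Bayesian power may also change, because the plan puts an "informative prior distribution on the control group where the mean and standard deviation are educated guesses". It cannot be recomputed, since the prior values are not stated.

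**4. Safety information on lorcaserin with cocaine.** The one-sided 95% upper bound on an event rate after zero events in n subjects is 1 − 0.05^(1/n). The chance of seeing at least one event with true rate p is 1 − (1 − p)^n; the rates p below are assumptions.

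| | n = 12 | n = 6 |
|---|---|---|
| Upper bound after zero events | 22.1% | 39.3% |
| P(at least one), p = 5% | 0.460 | 0.265 |
| P(at least one), p = 10% | 0.718 | 0.469 |
| P(at least one), p = 20% | 0.931 | 0.738 |

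**5. Within-subject PK precision.** The half-width of a paired 95% interval, in SDs of the within-subject difference, is t(0.975, n − 1)/√n.

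- n = 12: 0.635
- n = 6: 1.049
- Ratio: 1.049/0.635 = 1.65, whatever the SD.

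**The case against.** The strongest reply is that the sentence is ambiguous and not an error. It does not say respectively, it joins the arms with or, and 1:2 is the right ratio if placebo is taken first, as in Dosage/Dosage Regimen. Every explicit count in the plan agrees, and explicit counts should outweigh an unlabelled ratio. This stands as to intent: nobody reading the whole protocol would conclude that 6 on lorcaserin was planned. It does not make the sentence right. In the order it names the arms, it gives the reverse of the design, in the one place that specifies the computer-generated scheme.

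Other points:

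- **The harm is hypothetical.** This stands. Nothing in the documents shows that the list was reversed. The DSMB might also notice, since treatment-group data may be presented to it (Data Safety Monitoring, part b), but no check of the list against 12 and 6 is described.
- **Urn randomisation by gender** (Data Sets Analyzed; synopsis, Primary Analysis Plan) may mean that no fixed list exists. That affects how the check is made. It leaves the 12 and 6 target unchanged.
- **The factor 1.65 depends on the method.** This stands in part. The plan says only that PK parameters are compared within subjects. With an error term pooled over Days 2, 6 and 10, df = 2(n − 1), and the ratio is (2.228/√6)/(2.074/√12) = 1.52. Either way the interval is at least half as wide again.
- **Nothing is miscalculated.** True: the total is 18 throughout. The defect is a ratio that disagrees with the counts.

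**Conclusion.** The concern holds. The operative randomisation sentence, read in the order it names the arms, reverses the 12 lorcaserin and 6 placebo stated or used everywhere else that arm sizes appear. The likely cause is transposed labels, and the intended allocation is not in doubt.

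The consequence is conditional on the scheme having been built literally from that sentence. In that case planned exposure to the combination halves, with the losses in safety information and PK precision shown above. The factor 1.65 assumes a paired t interval. Unchanged t-test power assumes equal variances. The 12 and 6 are planned numbers: withdrawals are replaced (Replacement of Subjects), which could raise the number exposed under either split.

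This should be fixed. The sample size and the planned analyses are unaffected by the correction.

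**What to change.** In Method of Assigning Subjects to Treatment Groups, state the ratio with labels and counts: lorcaserin:placebo 2:1, 12 lorcaserin and 6 placebo. Have someone independent of the blinded team check the generated list against 12 and 6. If the urn procedure leaves no fixed list, check the target allocation programmed into the scheme.

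The cost is a one-line correction and one check. No patients, procedures or analyses are added.
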